9. POTENTIAL BENEFITS

No immediate or direct benefits to patients participating in this study are expected. However, it is possible that participants will learn more information about epilepsy and have improved adherence. The information obtained from this study can ultimately be used to increase knowledge in the scientific community about how to improve adherence in diverse youth with epilepsy.

10. POTENTIAL RISKS, DISCOMFORTS, INCONVENIENCES, & PRECAUTIONS

There are minimal potential risks/discomforts/inconveniences to participants in this study, no greater than those encountered in routine behavioral assessment and clinical care. There are no medical risks. All the questionnaires have been used in research, including our own, without any reported negative effects; however, it is possible that a small group may feel uncomfortable responding to questions. Participants may decline answering questions that cause them to feel uncomfortable and will be reminded of this prior to each study visit. Participants may also withdraw from the study at any time and will be informed of this right during the consent process.

If a participant is distressed by any study procedures, the site PI or designee (CCHMC- [name] or [name]., licensed clinical psychologists) at CCHMC will be contacted immediately to assess the situation. The study PI or their designee will provide appropriate referrals and/or intervention. In addition, questions on the questionnaires inquire about suicidal ideation by the caregiver, as well as the caregiver's perception of suicidal ideation for their child. These critical items are automatically flagged by the REDCap system, which will alert the clinical research coordinator at each site when a participant completes the questionnaire and endorses critical risk items. Safety procedures for suicidal ideation and reports of abuse/neglect are delineated in our safety monitoring committee plan (See Appendix G). In both cases and similar to above, the study PI or their designee at each site will be contacted immediately and he/she will assess the risk profile of the caregiver and/or child participant with subsequent recommendations based on the level of risk.

There is also the risk of possible loss of privacy of data or loss of confidentiality. These risks are inherent in all research studies, and a statement to this effect will be included in the informed consent. Every effort will be made to ensure that all participant information will be kept confidential. A majority of this study is going to be conducted via mHealth. Participants will be accessing or receiving information from several different sources, including REDCap, education/problem solving modules Wordpress site, Zoom for healthcare for Problem-solving with a therapist, a portal created by CCHMC to receive push notifications related to their adherence feedback reports, and the adherence monitoring portals for AdhereTech and SimpleMed. For each of these sites, we will use the participant's ID number and not their name. For example, enrolled participants will be assigned a secure login ID and password by the study staff to access measures via REDCap. Each site will only be able to see their own site's participants in REDCap, with the exception of the lead site (CCHMC). Participants will be asked not to share their ID or password with anyone else. Use of Protected Health Information (PHI) on online measures will be minimized and participants will not be asked to enter their last name, date of birth, or medical record number on the online measures. When the study is complete, the content of the site will be taken down. Setup is consistent with HIPAA guidelines and was designed to support projects that contain PHI and are subsequently subject to compliance with federal and state regulations regarding data of this type. Similarly, the Wordpress site for the modules will be linked to their study ID and there will be no identifying information listed in this site. However, for the individual adherence feedback reports, participants will be asked to provide a cell phone number to receive push notifications. Similarly, although Zoom-healthcare is HIPAA compliant, participants will be required to log-in to the secured Zoom server for Problem-solving sessions. This information and protection of the participant's identify will be clarified in the informed consent and assent forms.

Additionally, we will be geocoding their home address to quantify if the patients live in rural or medically underserved areas using a combination of HRSA maps and an app created by CCHMC. We will obtain parental permission to use the patient's address for this purpose.

Finally, to communicate study related information across sites, our team will be using trello, a task management system that is frequently used by research teams. No identifying information will be entered into the trello system; however, we will be tracking participants through the study procedures using their study ID.

Notably, the only place the study ID will be linked to the name and demographics is the participant database, which is password protected, individually, at each site by the research team. No other individuals outside of the IRB-approved research team will have access to this participant database and these databases will NOT be shared across study sites.

11. RISK/BENEFIT ANALYSIS

There is minimal risk associated with study participation. If participants feel distressed as a result of their participation, they will be encouraged to discontinue. The PI ([name]) and site PIs or their designee will be available to participants during study participation to assess for discomfort, safety, and risk, as needed. The minimal risks of this study do not outweigh the potential indirect benefits that may be gained through increasing knowledge about best practices for improving adherence to treatment and quality of life of children with pediatric epilepsy.

12. DATA SAFETY AND MONITORING

This is a multisite observational study and is considered minimal risk. A Safety Monitoring Committee (SMC) is in place for this study and will review randomization, safety events, and study progress every 6 months following trial initiation. In addition, each site's research team will monitor for safety and adverse events at each study visit. The SMC plan, which was approved by the National Institutes of Nursing Research, is attached in Appendix G. [name] (PI) and site PIs, and the members of the Data Safety Monitoring Plan will be responsible for monitoring the

safety of participants and complying with all reporting requirements. Any serious adverse events will be reported immediately to the IRB as required by the hospital's policy, as well as NINR.

13. PRIVACY AND CONFIDENTIALITY

All study personnel have been trained in data safety and monitoring, privacy and confidentiality, minimizing risks related to loss of privacy and confidentiality. We will closely monitor performance of our research personnel to ensure the strictest standards. Additional information related to privacy and confidentiality is noted above in section 10.

13.1 Data De-Identification: All data will be de-identified with the use of unique assigned study identifier codes. No other identifying data such as address, phone numbers, social security number, or zip code will be entered on electronic measures. Electronic data files (including downloads of data from REDCap measures) will only identify participants via study identifier codes and will be password protected. Electronic data files will be maintained on CCHMC hard drives.

Because this research study involves payment for participation, we are required by Internal Revenue Service (IRS) rules to collect and use participant's social security number (SSN) or taxpayer identification number (TIN) in order to track the amount of money that we pay them. Unless they have given specific permission for another use of their SSN or TIN related to this research study, we will only use their SSN or TIN to keep track of how much money we pay them and their SSN or TIN will not be used as part of this research study.

13.2 Data Storage and Management: Informed consent documents and all electronically collected data will be maintained in REDcap, a secure web-based platform, and in a password-protected electronic database on CCHMC hard drives. Although CCHMC, as the Primary Site, will be the study management location, no patient information from other sites will be shared other than de-identified IDs. Paper informed consent documents will be maintained in locked storage cabinets, if they are needed, and will be kept separate from participant data.

Deidentified adherence data will be stored on their respective portals (AdhereTech, SimpleMed) and these data will be triangulated with a CCHMC developed portal to provide individualized adherence feedback reports, based on the participant's cell phone number.

Trello (www.trello.com), a web-based project management tool, will be used to coordinate study-related tasks across sites. No identifiable patient information will be saved in this platform. Medical chart data will be collected by trained study staff under the supervision of the PI. These risk protection methods have been effectively used by the PI and her collaborators for numerous studies.

Individual data will not be available to anyone not directly associated with the study. All study personnel have been trained in data safety and monitoring, privacy and confidentiality, minimizing risks related to loss of privacy and confidentiality. We will closely monitor performance of our research personnel to ensure the strictest standards. Study-related information will not be released without written permission of the participant.

14. COST OF PARTICIPATION

There are no costs for participation in this research study. Participants will be responsible for the usual costs of medical care.

**Epilepsy Adherence in Children and Technology (eACT): Fostering
Medication Adherence in Children With Epilepsy Using mHealth
Technology**

Clinicaltrials.gov NCT03817229

Unique Protocol ID: 2018-8411

Version 1.0-5/20/25

Power and Sample Size Estimation

Sample size estimation was informed by results of previous studies of adherence interventions. Effect sizes for education-focused adherence interventions with reminders in other chronic conditions relative to controls (e.g., treatment as usual, pre-post) range from 0.08-0.20 [42, 43], while those with adherence feedback range from 0.78-1.03 [44, 45]. Specifically, an HIV study found that individualized adherence feedback demonstrated a large, standardized effect size (Cohen's $d=0.78$) [44]. Similar and higher effect sizes have been found for mHealth interventions that include education, automated digital reminders, or individualized feedback in adult samples including asthma, diabetes, and heart disease (Cohen's $d=0.70-2.51$) [46-48].

Given the range of observed effect sizes and taking into account the size of clinically meaningful changes in adherence, sample size was determined to detect a small-to-moderate standardized effect size (Cohen's $d=0.36$) for the primary analysis of SMART Stage 1 comparing intervention to control with 80% power with significance level 0.05. Assuming 2:1 randomization to intervention vs control yields a conservative total sample size estimate of 270, with ~180 participants randomized to intervention and ~90 to control. This sample size leads to 97% power to detect a moderate standardized effect size (Cohen's $d=0.50$).

Power for the secondary analysis involving pairwise comparison of the intervention strategies embedded in the SMART is informed by effect sizes for our face-to-face problem-solving adherence intervention, which incorporates individualized adherence feedback relative to treatment as usual. These effect sizes ranged from from 0.95 (1st problem-solving session) to 1.59 (2nd problem-solving session). Power analyses for comparison of intervention strategies require additional unknown assumptions, such as the anticipated response rate to intervention at the end of Stage 1. Assuming a 50% response rate to SMART Stage 1 intervention and a Bonferroni multiplicity adjustment, the proposed sample size provides 80% power with significance level 0.05 to detect a standardized effect size of $d=0.69$ between any pair of the embedded intervention strategies #1 - #3.

To achieve the proposed sample size, the planned study sample was 600 participants across sites, with the goal of approximately 330 of the 600 being randomized (i.e., 10% attrition during the baseline phase, and 45% would be > 95% adherent, completing the study before randomization) [5]. Following initial randomization, these ~300 participants were to be assigned in a 2:1 ratio to intervention ($n=200$) and control ($n=100$). Making a conservative assumption of 10% attrition of participants in each initial SMART intervention arm results in anticipated $n=180$ randomized to intervention and $n=90$ randomized to control at the end of Stage 1. However, per federal and institution specific guidelines, recruitment was suspended during the COVID-19 pandemic, and the study team determined that 450 participants would need to be enrolled for $n=180$ to be randomized to the intervention arm and $n=90$ randomized to the control arm.

Statistical Analysis Plan

Primary Analysis Plan:

An intent to treat approach will be undertaken for all analyses, and a significance level of 0.05 will be used. The primary analysis examines the efficacy of the mHealth adherence intervention in caregivers of youth (ages 2-12) with newly diagnosed epilepsy (< 2 years) on electronically monitored adherence relative to control on the basis of the primary outcome of change in electronically monitored adherence from baseline, calculated using the baseline and final 30-day adherence. The primary hypothesis is that participants initially randomized to intervention will exhibit significantly greater improvements in adherence compared to those randomized to control from baseline to end of Stage 1. Although sample size was calculated conservatively based on use of a two-sided, two-sample t -test with unequal sample sizes, to achieve a more efficient analysis with enhanced power, the primary analysis will be based on a standard analysis of covariance with adherence at the end of Stage 1 as the dependent variable and baseline adherence as the covariate.

Secondary Analysis Plan:

Secondary analyses will compare the mean outcomes associated with each of intervention strategies #1 - #3 embedded in the SMART on the basis of the outcomes adherence, seizure severity/frequency, HRQOL, and healthcare utilization at 1-, 6-, and 12-months post-intervention. Strategies #1 and #2 are non-adaptive intervention strategies in that intervention is not modified in accordance with Stage 1 adherence status (or any other participant characteristics), while #3 is an adaptive intervention strategy in that intervention is augmented by problem-solving in Stage 2 only under non-adherence in Stage 1. The pairwise comparison of the non-adaptive strategy #1 to the adaptive strategy #3 represents comparison of the least resource-intensive strategy (control) to the most resource-intensive strategy. Comparison of strategies #1, #2, and #3 will be carried out using specialized methods for SMART analysis based on inverse probability weighting for estimation of the mean outcome associated with a strategy that account for the fact that actual experiences of participants may be consistent with more than one strategy; for example, a participant who is randomized to intervention in Stage 1, is adherent in Stage 1 (i.e., is a responder to intervention), and continues to receive intervention in Stage 2 is consistent with having followed either embedded strategy #2 or #3. In this case, a participant's data contributes to assessment of improvement in outcome for both strategies. For each strategy, the inverse probability weighting is by the reciprocal of the estimated probability that a participant's experience is consistent with the strategy. We will conduct pairwise comparisons of the three embedded strategies using these methods based on adherence, seizure severity/frequency, HRQOL, and healthcare utilization at 1, 6-, and 12-months post-intervention. We will also conduct a global test of the null hypothesis that the mean outcomes associated with the three strategies are the same versus the alternative that at least one mean differs from the others.

Exploratory Analysis Plan:

The data collected will provide a rich resource for exploratory analyses investigating participant baseline characteristics and post-randomization characteristics ascertained prior to assessment of Stage 1 adherence status that can inform tailored selection of initial intervention (intervention or control) and of subsequent intervention for non-adherent individuals receiving initial intervention (continue intervention or augment intervention with problem solving). We will use standard methods to evaluate whether baseline characteristics moderate participants' adherence status following initial intervention, including tests for qualitative interactions. Evaluation of moderators of outcomes at Stage 2 and at 1-, 6-, and 12-months post-intervention is complicated by the sequential nature of the interventions, requiring the use of specialized statistical methods, such as Q-learning and value-search estimation. We will also use these methods to estimate an optimal adaptive intervention strategy for individualizing selection of initial intervention and intervention in the case of non-adherence based on baseline and evolving child/family characteristics, informing strategies for future study.

Handling of Missing Data:

Missing change in adherence outcomes in the primary analysis will be addressed in several ways. Under the assumption that the adherence outcomes are exactly normally distributed and linearly related, the analysis of covariance based on the complete cases will yield valid inferences under the assumption of missing at random (MAR). To evaluate the evidence in the data under MAR without making the restrictive assumptions of normality and linearity, we will conduct the complete case analysis if missingness is nondifferential by Stage 1 assignment and less than 10% in each assignment group. To assess sensitivity of this analysis to missingness, under the assumption of MAR, we will also conduct an inverse probability weighted complete case analysis of covariance in which outcomes are weighted by the reciprocal of the estimated probability not dropping out of the study in Stage 1 based on a

logistic regression model that incorporates baseline variables associated with failure to complete Stage 1.

For the secondary analyses, Stage 2 and later outcomes will be assumed to be missing according to a MAR mechanism. If the extent of missingness is less than 10% for each strategy, we will conduct complete case analyses comparing the embedded intervention strategies. To assess sensitivity of these analyses to missingness and to obtain a definitive analysis if the extent of missingness is greater than 10%, under the MAR assumption, we will use inverse probability weighting of complete cases in estimation of the mean outcomes associated with each strategy, where the outcomes are weighted by the reciprocal of the estimated probability not dropping out of the study/having the outcome observed as a function of baseline and previously observed variables based on logistic regression.

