5. DURATION

The anticipated duration of the study is approximately 5 years. The duration for participants is variable depending on their level of adherence during the baseline period and their enrollment date as the follow-up period was shortened twice to continue enrollment and allow participants to complete the study by the end of the grant period.

- For enrolled participants who achieve electronically monitored adherence >95% in the baseline period, their study participation will be approximately 2 months, with conclusion at the end of the baseline period.
- For participants with adherence < 95% in the baseline period, their participation will be:
 - 20 months (2 months baseline, 5 months of active intervention, and 13 months of follow-up) if they enrolled before 12/9/2022.
 - 14 Months (2 months baseline, 5 months of active intervention, and 7 months of follow-up) if they enrolled between 12/9/2022 and 3/8/2023.
 - 8 months (2 months baseline, 5 months of active intervention, and 1 month of follow-up) if they enroll after 3/8/2023.

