- **Automated Digital Reminders** – Each adherence electronic monitor has the capability to provide automated digital reminders. As a part of the intervention, all caregivers randomized to intervention will have the option of selecting the type of automated digital reminders that they receive, which could include text messages and/or device sounds/lights. These will be turned on immediately following the baseline period based on the participant's preferences.
- **Individualized Adherence Feedback Reports** - Individualized adherence feedback will be received by families once a week where they will be provided with information about

adherence levels over the previous 7 days based on their electronic adherence monitors. All individualized adherence feedback reports will be received on Monday. A separate portal has been developed by Bioinformatics at CCHMC to create the adherence feedback reports. Data from the SimpleMed pillbox via open API and AdhereTech via excel spreadsheets are merged to provide a calendar plot with the participant's adherence data from the past week. The participant will receive a push notification to view their adherence from the past week. The portal with this information will use the same log-in information as the education and problem-solving sessions. It is notable that the participant must provide a cell phone number for the push notifications.

At the beginning of SMART Stage 2 (2-months), caregivers randomized to the treatment group who demonstrate continued non-adherence (<95%; non-response) by the end of Stage 1 will undergo a second randomization to either 1) continued individualized adherence feedback or 2) individualized adherence feedback augmented with a mHealth problem-solving module and two therapist-guided sessions using Zoom for healthcare. The mHealth problem-solving module incorporates a video and reviews skills of problem-solving for caregivers of young children with epilepsy and takes approximately 10 minutes to view from any mobile device, tablet or computer. The same log-in information for the education microlearning sessions will be used to access the problem solving modules. Following completion of the problem-solving module, a therapist will contact the family to review and apply the problem-solving skills. Two sessions will occur one month apart via teleconferencing (i.e., Zoom for Healthcare-Appendix D), which is a HIPAA-compliant teleconferencing site.

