After completion of Stage 2, automated digital reminders will be turned off and adherence feedback reports will cease to be provided. Additional questionnaires will be completed via REDCap at Post-Treatment (1-Month Follow-Up in Month 8), Follow-Up 1 (6 months post-treatment in Month 14)*, and Follow-Up 2 (12 months post-treatment in Month 20)**.

Data collection procedures and measures: Participants will complete a demographic questionnaire that provides general information about the child's age, caregiver work history, family composition, socio-economic status, family history of seizures, history of seizures (e.g., type, who witness, when they occurred), and comorbid illnesses (e.g., learning disorders). In addition, caregivers will complete the questionnaires detailed in the table below.

Construct Measured	Respondent C=Caregiver; M=Medical Chart Review D=Doctor/Clinician	Stages and Time points			
		Baseline	Post (1 month post- treatment)	Follow-Up 1 (6 months post- treatment) *	Follow-Up 2 (12 months post- treatment) **
ORDER OF MEASURES (As applicable)					
Background Form (Demographic)	C	X			
Pediatric Epilepsy Medication Self-Management Questionnaire (PEMSQ) 
 PEMSQ: Self-reported Adherence 	C	X	X	X	X
Behavior Assessment System for Children-3 Parent-Rating Scales	C	X	X	X	X
Short Test of Functional Health Literacy in Adults	C	X	X	X	X
Pediatric Quality of Life in Epilepsy Module	C	X	X	X	X
Brief Symptom Inventory-18 (BSI-18)	C	X	X	X	X
Epilepsy Knowledge Questionnaire-Adapted (EKQ)	C	X	X	X	X

Social Problem-Solving Inventory-Revised Short (SPSI-Revised Short)	C	X	X	X	X
Pediatric Epilepsy Side Effects Questionnaire (PESQ)	C	X	X	X	X
Seizure Severity Scale Adapted for Children (SSSC)	C	X	X	X	X
Family Assessment Device (FAD)	C	X	X	X	X
Global Assessment of the Severity Scale of Epilepsy in Children (GASE)	D	X	X	X	X
Healthcare utilization	C	X	X	X	X
Medical Chart Review	M	X	X	X	X
Feasibility/Acceptability Questionnaire (FAQ)	C		X		
Impact of COVID-19 on Pediatric Epilepsy Management (ICPEM)	C	X	X	X	X

*Follow-Up 1 Questionnaires will only be completed by participants enrolled before 3/8/2023

**Follow-Up 2 Questionnaires will only be completed by participants enrolled before 12/9/2022

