8.1 Sample Size Considerations and Power Analysis: Power analysis was conducted based on SMART Stage 1, assuming ~180 participants randomized to treatment and ~90 to control group. Effect sizes for education-focused adherence interventions with reminders in other chronic conditions relative to controls (e.g., treatment as usual, pre-post) range from 0.08-0.20,^{72,170} while those with adherence feedback range from 0.78-1.03.^{80,171} Power for the primary analysis (Aim 1 below) will be 80% to detect a small-to-moderate standardized effect size (Cohen's $d=0.36$) and 97% to detect a moderate standardized effect size (Cohen's $d=0.50$). These detectable effect sizes reflect clinically meaningful changes in adherence. Power analyses require known and unknown assumptions, such as the anticipated response rate to Education + Automated Digital Reminders + Individualized Adherence Feedback at the end of Stage 1. Effect sizes for our face-to-face problem-solving adherence intervention, which incorporates IAF relative to treatment as usual, ranged from 0.95 (1st problem-solving session) to 1.59 (2nd problem-solving session).¹⁵ Assuming a 50% response rate to SMART Stage 1 treatment and a Bonferroni multiplicity adjustment, the proposed sample size provides 80% power with alpha at 0.05 to detect a standardized effect size of $d=0.69$ between any pair of embedded strategies (SMART Stage 2).

8.2. Data Analysis: All data analysis and management will also occur at North Carolina State University (NC State), which is the primary data analysis site. The Division of Behavioral Medicine and Clinical Psychology at CCHMC has developed a Divisional Data Core (DDC) in cooperation with the divisions of Biostatistics and Epidemiology and Bioinformatics to share the de-identified data with NC State. The CCHMC DDC will provide quality reports to audit the data routinely, provide data for safety monitoring committee reports for the biostatisticians at NC State, and cleaning of the data.

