Aim 2: To compare the effectiveness of the three intervention strategies on adherence, seizure severity/frequency, quality of life, and healthcare utilization at 1-, 6-, and 12-months post-intervention. We will carry out secondary analyses to compare the three intervention strategies embedded in the SMART: #1 E+ADR (control), continuing regardless of response at three months; #2 E+ADR+IAF (treatment), continuing regardless of response; and #3 E+ADR+IAF+Problem-solving if not responsive. Strategies #1 and #2 are non-adaptive intervention strategies in that treatment is not modified in accordance with response status (or any other participant characteristics); #3 is an adaptive intervention strategy in that treatment is augmented by problem-solving only among non-responders. The pairwise comparison of the non-adaptive strategy #1 to the adaptive strategy #3 represents comparison of the least resource-intensive, least burdensome strategy to the most resource-intensive, most burdensome strategy. Note that the actual experience of a participant may be consistent with more than one embedded strategy; in particular, a participant who receives E+ADR+IAF initially, responds, and continues to receive E+ADR+IAF is consistent with having followed either strategy #2 or #3. Thus, such a participant's data contribute to assessment of improvement in adherence for both of these strategies. Comparison of strategies #1, #2, and #3 requires the use of specialized methods¹³³ that account for the fact that actual experiences of participants may be consistent with more than one strategy. We will conduct pairwise comparisons of the three embedded strategies on the basis of adherence, seizure severity/frequency, quality of life, and healthcare utilization at 1-, 6-, and 12-months post-intervention. Appropriate methods will be used based on the type of outcome measure: binary, count, and continuous variables.

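### The d=0.69 stated for any pair of embedded strategies is not the detectable difference for the planned strategy-mean contrasts, which is about 0.48 SD or less with three tests

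*SAP*

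**What the plan says.** The SAP (Power and Sample Size Estimation) gives the secondary power statement under two conditions: "Assuming a 50% response rate to SMART Stage 1 intervention and a Bonferroni multiplicity adjustment". On that basis it claims 80% power to "detect a standardized effect size of $d=0.69$ between any pair of the embedded intervention strategies #1 - #3". Protocol section 8.1 gives the same number with a stage label: "to detect a standardized effect size of $d=0.69$ between any pair of embedded strategies (SMART Stage 2". Neither power paragraph gives the Bonferroni divisor, the second-stage allocation ratio, or the SD that standardizes d.

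The contrasts themselves are defined elsewhere. The SAP's Secondary Analysis Plan estimates the mean outcome under each strategy by IPW, with treatment-arm responders counting towards both #2 and #3. It then states: "We will conduct pairwise comparisons of the three embedded strategies using these methods based on adherence, seizure severity/frequency, HRQOL, and healthcare utilization". These comparisons are repeated at three follow-up times: one, six and twelve months after the intervention.

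Only one Stage 1 arm is re-randomized. Protocol section 8 says that "caregivers randomized to the treatment group who demonstrate continued non-adherence (<95%; non-response) by the end of Stage 1 will undergo a second randomization". Strategy #1 is described under Aim 2 in section 8.2 as "1 E+ADR (control), continuing regardless of response at three months".

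**The concern.** The power sentence names one quantity and the analysis estimates another. A difference between two strategy means averages over responders and non-responders. A difference between re-randomized arms concerns non-responders only. The two are on different scales, and the second does not exist for a pair that includes #1. A reader who takes 0.69 at face value would think that Aim 2 can reliably detect only fairly large differences between strategies. That reader also could not tell what difference was planned for #1 vs #3, the pair that both documents single out as least against most resource-intensive. What is at stake is how the Aim 2 results are read, in particular a null result.

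**Working it through.** **Inputs from the documents.** 180 treatment and 90 control at the end of Stage 1, with the planned 10% attrition already removed; 50% response; overall alpha 0.05; 80% power; Bonferroni adjustment.

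**Assumptions where the text is silent.** Two-sided tests (stated only for the primary test); divisor m = 3, one per pair; 1:1 second stage, so that 90 non-responders split 45 and 45; no further loss; control SD equal to the total SD in the treatment arm, set to 1.

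**Step 1: the plan's own figures.** The primary power reproduces. With 180 vs 90 at two-sided 0.05, power is 79.6% at d=0.36 and 97.2% at d=0.50. For 0.69, the multiplier is k = z(1 − 0.05/6) + z(0.80) = 3.236. A 45 vs 45 comparison gives 3.236 × √(2/45) = 0.682 by the normal formula and 0.693 by the t-test. Power at 0.69 is 81.0% and 79.5% respectively. Other inputs also land close: 45 vs 90 at 0.05/12 gives 0.687, and 60 vs 30 at 0.05/2 gives 0.699 (both t-tests).

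**Step 2: the planned contrasts.** Let f be the share of treatment-arm variance that lies among non-responders, with equal responder and non-responder means. Then f = 0.5 means equal SDs, and f = 1 means responders do not vary. At 1:1:

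- Var(#2) = Var(#3) = (1+f)/180
- Var(#1) = 1/90
- Var(#2 − #3) = 4f/180, because the shared responders cancel

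Detectable difference = k × √variance, for m = 3:

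| Contrast | f = 0.5 | f = 1 |
|---|---|---|
| #1 vs #2, #1 vs #3 | 3.236 × √(1/90 + 1.5/180) = 0.451 | 3.236 × √(1/90 + 2/180) = 0.482 |
| #2 vs #3 | 3.236 × √(2/180) = 0.341 | 3.236 × √(4/180) = 0.482 |

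Simulation of IPW means with estimated weights (8,000 runs per point) agrees. For #1 vs #3, power is 80.0% at 0.45 (f = 0.5) and 78.4% at 0.48 (f = 1).

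**Step 3: a responder/non-responder mean gap.** The SAP uses estimated probabilities as weights. The gap between responder and non-responder means then drops out of #2 vs #3, although it still adds to the total SD. With equal within-group SDs and a gap g in total-SD units, the non-responder variance is 1 − g²/4, and Var(#2 − #3) = 0.25 × (1 − g²/4) × 2/45. This gives 0.30 at g = 1 and 0.23 at g = 1.5. So 0.34 is not a floor for this pair.

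**Step 4: other divisors and ratios.**

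- m = 36 (3 pairs × 4 outcomes × 3 times): k = 4.039. The #1 pairs become 0.563 to 0.602. #2 vs #3 becomes 0.426 to 0.602 with equal means, or about 0.63 by simulation at the top end.
- At 1:1 and f = 1, reaching 0.69 takes a divisor of about 328.
- An assumed 2:1 second stage with f = 1 gives at most 0.539 for m = 3 and 0.673 for m = 36.

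**Step 5: power at a true strategy-mean difference of 0.69.** With m = 3, the lowest value is 98.7% by formula and 98.2% by simulation. With m = 36, it is 92.4% and 88.1%.

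**The case against.** The best defence is that 0.69 is not an arithmetic error. It can be reproduced, and quoting one cautious value for several contrasts is a common planning shortcut. Read as an upper limit on the detectable difference, the sentence is true at full sample size. The effects cited as motivation, 0.95 to 1.59, exceed it in any case. All of this stands, and it is why the point is minor. It does not rescue the label, because the sentence calls 0.69 a difference between strategies. With equal SDs and means, a non-responder effect of 0.69 is 0.5 × 0.69 = 0.345 on the strategy-mean scale.

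Several stronger readings are tempting, and the documents do not support them:

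- **Aim 2 is underpowered.** The discrepancy runs the other way: the design detects smaller differences than stated.
- **The sponsor used the wrong test.** The 45 vs 45 origin is only inferred, and other inputs give nearly the same number.
- **The second-stage ratio is missing from the plan.** Protocol Figure 1 illustrates the design but is absent from the text available here, so it may carry the ratio.
- **Shortened follow-up explains 0.69, or the sentence hides its sample size.** Both documents tie the figure to the proposed sample size. Protocol section 5 does say that "the follow-up period was shortened twice to continue enrollment", and a table footnote in section 8 says "Follow-Up 2 Questionnaires will only be completed by participants enrolled before 12/9/2022". That lowers later sensitivity but is a separate matter. With three tests and equal loss in all groups, 0.69 for the #1 pairs would correspond to only (0.451/0.69)² = 43% to (0.482/0.69)² = 49% of participants followed.
- **0.34 to 0.48 is the correct replacement range.** It depends on SDs and means that the documents do not give. High responder adherence does not make 0.48 the likelier value for #2 vs #3, since it also implies a mean gap. Assuming responders at 97.5% (SD 1.5), with non-responder means of 60 to 85% and SDs of 10 to 25, that pair spans 0.17 to 0.45.

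**Conclusion.** The power sentence is wrong as written, at minor severity. Under the stated assumptions, the #1 contrasts are detectable at about 0.45 to 0.48 total SDs. The documents' figure is therefore too large by a factor of 0.69/0.482 = 1.4 to 0.69/0.451 = 1.5. For #2 vs #3 the detectable difference is at most about 0.48. It is 0.34 with equal SDs and means, and lower if the means differ and the weights are estimated. The exact values rest on the assumed ratio, divisor and variance split. The conclusion that 0.69 is not the strategy-mean figure does not: even 36 tests, a 2:1 second stage and all variance among non-responders together reach only 0.67. If 0.69 is the non-responder comparison, it cannot describe any pair that includes #1. The misstatement is conservative and confined to a secondary analysis.

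**What to change.** In the SAP power section and in protocol section 8.1, replace the single figure with the detectable strategy-mean difference for each of the three pairs. Compute it for the IPW estimator with the sponsor's own divisor, second-stage ratio and SD assumptions, and state those inputs. If 0.69 came from the comparison of the two re-randomized non-responder groups, keep it under that name and in non-responder SD units. The figures above are illustrative and should not be copied in as fixed values. The cost is two or three sentences in each document; design, alpha, estimator, sample size and primary analysis do not change.
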